### 9.2.2 Safety Analysis

All AEs will be listed, tabulated and summarized by event, number and percent of cases/subjects. AE rates and 95% confidence intervals will be presented.

For categorical variables, such as radiographic stability, the number and percent in each category will be presented.

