#### 2.2 Safety

All operative site events as well as all serious adverse events (SAEs), excluding elective procedures, will be collected and compared to the historical control group and to published data. It is expected that the AE rates reported for hips implanted with the Tritanium® Acetabular Shell will be comparable to those reported in the literature for similar porous coated cementless acetabular shells and for the historical control group. Details regarding AE definitions, recording and reporting are in Section 8 of this protocol, Adverse Events.

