#### 7.4 Annual Follow-up Visits

Clinical data will be collected via office visit by the investigator at the following annual postoperative intervals: 1-year, 3-year and 5-year. Tools for postoperative evaluation will be the HHS, AP hip, AP pelvis and lateral radiographs.

Patient outcomes data will also be collected via patient questionnaires. At each of the 1-year, 3-year and 5-year follow-up visits, the SF-12, LEAS and EQ-5D are required. These same questionnaires are also required at 2-year and 4-year intervals, and may be completed during an office visit or sent to the subject to be completed, initialed and dated and returned to the investigative site.

All clinical data, radiographs, and patient outcomes data must be collected within  $\pm$  2 months of the 1-year and 2-year anniversary dates. For remaining annual time points, the window expands to  $\pm$  3 months of the 3-year anniversary date and  $\pm$  4 months of the 4-year and 5-year anniversary dates.

The initial phase of the study will continue for 5 years after surgery and include collection of the previously described radiographs, HHS, and SF-12, LEAS and EQ-5D patient questionnaires. In the second phase of the study, all subjects will complete a brief satisfaction questionnaire annually at the 6-year, 7-year, 8-year, 9-year and 10-year follow-up intervals. This form may be completed by the SC during a patient telephone interview, or by the patient either at home or during a clinic visit. The questionnaire will be used to obtain the following information, at a minimum:

- Patient satisfaction with the hip replacement
- Presence of any pain in the study hip
- Any surgeries performed on the study hip

The questionnaire will also provide information on any revisions and enable calculation of the Kaplan-Meier survival curve necessary to meet the primary endpoint of the study.

Additionally, at investigational sites that choose to continue collecting clinical and radiographic data during the second phase of the study, subjects will be evaluated again at 7 and 10 years after surgery.

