### **8 Adverse Events**

### 8.1 Reporting of Adverse Events

The AE reporting requirements for this study are as follows:

- All AEs that meet the definition of serious, excluding elective procedures
- All AEs related to the operative site, regardless of seriousness

Elective procedures meeting the definition of an SAE do not need to be reported as AEs according to this study protocol. Examples of such elective procedures include, but **are not limited to**, the following commonly seen events:

- Contralateral THR
- Total Knee Replacement
- Rotator Cuff Surgery
- Cataract Surgery

[figure not shown]
Such events will not be captured on the AE electronic Case Report Form (eCRF) but rather will be captured on the postoperative functional evaluation at the 6-week, 1-year, 3-year, and 5-year, time points. Additional events of this nature will be captured on the 7-year and 10-year functional evaluations if the investigator chooses to bring subjects in for these optional visits. On these functional evaluations, investigators and SCs will be prompted to question subjects as to whether they have seen a doctor for any reason, been hospitalized for any reason or have a current impediment to their function.

Additionally, SCs will be responsible for following up with the subjects regarding any questionable responses received on the satisfaction questionnaire administered in postoperative years 6 through 10. If it is determined upon this further investigation that a protocol-defined adverse event has occurred, the SC will be responsible for completing an AE eCRF and submitting the event to the sponsor, and reporting to the IRB as required.

The following decision tree facilitates identification of AEs for which reporting is required under this study protocol:

Figure 1

Adverse Event Decision Tree

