#### Adverse Event Reporting Period

The study period during which AEs must be reported is normally defined as the period from the initiation of any study procedures to the end of the study treatment follow-up. The start of study procedures is considered to be the point of consent. Any AEs which fit the protocol defined reportable events must be reported from the time of consent until study completion.

At each contact with the subject the investigator must seek information on AEs by specific questioning and, as appropriate, by examination. Information on protocol defined AEs should be recorded immediately in the source document and also in the appropriate AE module of the eCRF. All clearly related signs, symptoms and abnormal diagnostic procedure results should be recorded in the source document and grouped under one diagnosis as appropriate. The clinical course of each event should be followed until resolution or until it is determined at the end of the study that the AE will not resolve.

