### 9.1.4 Primary Efficacy Analysis

A case success is defined as no incidence of revision or removal of the acetabular component within 5 years. A 90% confidence interval of the success rate will be computed at 5 years postoperative. If the lower bound of this confidence interval is greater than 94%, the non-inferiority hypothesis will be supported. If the lower bound of this confidence interval is above 99%, the superiority hypothesis will be supported. The Kaplan-Meier survival curve of revision or removal of the acetabular component will also be displayed using SAS/PROC LIFETEST.

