#### 9.4.2 Sample Size Calculation

A literature review shows that at 5 years of follow-up there is a 97.9% to 99.6% success rate in similar devices using revision or removal of the acetabular component as the defining factor. Based on these results, it should be a reasonable assumption that the base success rate of revision or removal of the Tritanium® Acetabular Shell will be approximately 99% at 5 years. Using a base success rate of 99% from the literature and a delta of 5%, it was calculated that 142 total cases implanted with the Tritanium® Acetabular Shell would be needed to prove non-inferiority with 95% power. With a minimum of 142 cases analyzed, the primary hypothesis of the study will be met if the lower bound of the 90% confidence interval for the 5-year success rate is greater than 94%. By factoring in a 20% lost to follow-up rate within a 5-year period, the required sample size increases to 177 cases. Cases will continue to be enrolled until a total of 240 cases are implanted with the Tritanium® Acetabular Shell; half of these cases will use the X3® polyethylene insert alone as the bearing surface and the other half will use the MDM™ liner coupled with a compatible ADM/MDM™ X3® insert as the bearing surface.

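### Adverse event rates are to be compared with the historical control and published rates, but the planned summary fixes no time point and ignores unequal follow-up

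*Combined protocol and SAP*

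**What the plan says.** **The comparison.** Section 2.2 says that operative-site events and serious AEs (SAEs), excluding elective procedures, "will be collected and compared to the historical control group and to published data", and expects comparable rates. Section 12.3 repeats the aim against published rates. Section 9.4.1 announces statistical comparisons for safety variables without naming a method.

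**The summary.** Section 9.2.2: "All AEs will be listed, tabulated and summarized by event, number and percent of cases/subjects". The next sentence adds AE rates with 95% confidence intervals. It does not say whether a rate is per case, per subject or per person-year, or to what time it runs.

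**The period.** Under Adverse Event Reporting Period, reportable AEs "must be reported from the time of consent until study completion". Section 3.4 follows each case to 10 years. Section 9.1.5 puts AEs found through the year 6-10 questionnaire into the safety analysis.

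**Revision.** Section 9.1.4 defines success as no acetabular revision or removal within 5 years: "A 90% confidence interval of the success rate will be computed at 5 years postoperative". Sections 7.4, 9.1.5 and 9.4.1 plan a Kaplan-Meier analysis that continues through years 6-10. Section 9.2.1 also lists revision or removal as a safety parameter, without pointing to that analysis.

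**The concern.** The percentage of implanted cases that have ever had an event can only rise with follow-up, and it is pulled down by cases that leave early. Two groups with the same underlying risk will show different percentages if they were observed for different lengths of time or lost at different rates.

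Exposure will vary within this study. Section 9.4.2 allows for 20% loss by 5 years, and under section 10.3 death, withdrawal and shell revision all end participation. Publications are planned at 3, 5 and 10 years (section 16), so the percentage will also depend on the data cut. The other comparisons have a time point: HHS, SF-12 and LEAS at 1, 3 and 5 years, and revision at 5 years. AEs have none.

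At stake is whether a higher or lower AE percentage than the comparator's can be read as a property of the shell.

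**Working it through.** **1. The plan's own figure.** No stated figure belongs to the AE comparison. The only design calculation is for revision at 5 years: "Using a base success rate of 99% from the literature and a delta of 5"%, with 142 cases that "would be needed to prove non-inferiority with 95% power". With p0 = 0.94, p1 = 0.99 and one-sided alpha 0.05:

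- n = [(1.645·√(0.94·0.06) + 1.645·√(0.99·0.01)) / 0.05]² = 122.9
- with continuity correction, (n/4)·[1 + √(1 + 2/(n·0.05))]² = 142.2, matching 142
- 142/0.8 = 177.5, against 177 stated

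The figure reproduces and is tied to a 5-year horizon. The revision endpoint therefore has the fixed time that the AE summary lacks.

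**2. Follow-up alone, no losses.** The yearly rates are assumptions. Cumulative risk = 1 − exp(−h·t).

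| h per year | 5 years | 10 years | ratio |
|---|---|---|---|
| 0.5% | 2.5% | 4.9% | 2.0 |
| 1% | 4.9% | 9.5% | 1.9 |
| 2% | 9.5% | 18.1% | 1.9 |

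**3. With losses.** The 20% loss by 5 years comes from section 9.4.2; its continuation to year 10 and the 5-year risks q are assumptions. With λ = −ln(1−q)/5 and μ = −ln(0.8)/5, the crude proportion of all implanted cases with an event by time t is λ/(λ+μ)·[1 − exp(−(λ+μ)t)].

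Example, q = 5%: λ = 0.01026, μ = 0.04463, λ/(λ+μ) = 0.187. At 5 years, 0.187·(1 − 0.95·0.8) = 4.5%. At 10 years, 0.187·(1 − 0.76²) = 7.9%.

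| true 5-year risk | crude, 5 years | crude, 10 years | ratio | 10 years, half of post-year-5 events missed |
|---|---|---|---|---|
| 5% | 4.5% | 7.9% | 1.8 | 6.2% |
| 10% | 9.0% | 15.5% | 1.7 | 12.2% |
| 20% | 18.0% | 29.5% | 1.6 | 23.8% |

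Losses pull the crude 5-year figure below the true risk in every row. Incomplete capture after year 5 would partly offset the effect of longer follow-up.

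**4. Effect on a reading of the interval.** Take 240 cases counted to 10 years, an exact 95% interval, and a comparator fixed at its crude 5-year value with the same hazard. The chance that the study's lower limit lies above the comparator is 62%, 84% and 99% for the three rows. With both counted to 5 years it is 2.4%, 1.6% and 2.2%.

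**5. Early clustering.** Let H = −ln(1−q), with 80% of H in year 1 and the late rate continuing unchanged. The later rate is 0.2H/4 per year, so the 10-year total is H + 5·(0.2H/4) = 1.25H. For q = 5% the 10-year risk is 6.2% (ratio 1.24); for q = 10% it is 12.3% (ratio 1.23).

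In this pattern, rates per person-year over unequal periods also differ, in the other direction: the average hazard is 1.25H/10 over 10 years against H/5 over 5 years, a ratio of 0.625 (ignoring losses). Person-time rates therefore need a common horizon too.

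**The case against.** The strongest reply is that no mismatch with the main comparator has been shown. The synopsis says that the Trident X3 study's follow-up intervals and data closely match this one, and its length is not given. The background series with a mean of 4.9 years and with 8 to 10 years (section 1.1) are not named as AE comparators. No formal AE test or decision rule is specified, and the synopsis speaks only of reviewing complications. All of this stands. It limits the claim to a possible distortion, but does not supply the missing time point. Even with identical schedules, differential loss would matter.

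Four stronger readings are tempting, and the documents do not support them:

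- **Revision is also compared as a crude percentage without a horizon.** It is not. The endpoint and the literature benchmark (section 9.4.2) are both at 5 years, and a Kaplan-Meier analysis is planned. Only the cross-reference from 9.2.1 is missing.
- **Hospitalizations are no longer asked about after year 5.** The visit prompts on "whether they have seen a doctor for any reason, been hospitalized for any reason or have a current impediment to their function" serve events other than protocol-defined AEs. The postoperative eCRF (Appendix E) has a separate AE item. The year 6-10 form lists minimum content such as "Any surgeries performed on the study hip", but section 2.1.2 says it is meant to capture AEs. Coordinators must follow up doubtful answers (8.1), and AE questioning is required at every contact. What changes is mainly the mode of contact, and years 2 and 4 already allow mailed questionnaires.
- **Follow-up length drives the comparison, by a factor of two.** That needs a constant hazard and a 10-against-5-year contrast, neither of which the documents establish.
- **All comparisons should stop at 5 years.** That would block the synopsis's planned end-of-study comparison with long-term series.

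**Conclusion.** The point holds for AEs and not for acetabular revision. The plan promises a comparison of AE rates and specifies a summary that depends on how long, and how completely, cases are followed. This can distort the comparison; whether it will depends on the comparator's follow-up, which is not stated.

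The illustrative size, for identical hazards counted to 10 rather than 5 years, is a ratio of about 1.6 to 2 under a constant hazard and about 1.2 if events cluster early. These figures rest on assumed AE rates, 20% loss per 5 years extended to year 10 where losses are included, and a comparator counted to 5 years. A reader might infer that the safety objective cannot be answered at all. That goes too far: AEs are collected with onset dates, so a fixed-time summary is within reach. The primary endpoint is untouched.

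**What to change.** In section 9.2.2:

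- Report the cumulative incidence of first operative-site AE and first SAE at 1, 3 and 5 years with 95% confidence intervals, by Kaplan-Meier or a competing-risk estimate that treats death as a competing event. Rates per person-year over the same fixed periods are an acceptable alternative. State whether the unit is the case or the subject.
- Compare with the Trident X3 control at the same times, where its onset dates allow.
- Compare with published rates only at matching follow-up, including 10-year rates against long-term series.
- Tabulate years 6-10 separately, noting the change to mainly questionnaire contact.

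In section 9.2.1, refer the revision or removal item to the planned survival analysis.

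The cost is SAP wording and a few extra tables; the AE eCRF already records onset dates. The downside is that the control comparison depends on onset dates being available in the Trident X3 dataset. If they are not, that comparison should be labeled descriptive, with both follow-up lengths shown.

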### 9.3 Missing Data

No missing data will be imputed for the primary analysis and secondary analyses.

# 9.4 Statistical Methodology

### 9.4.1 Data Summary

The following is a detailed proposal of statistical analyses planned for data collected during the study.

Descriptive statistics will be computed for all preoperative conditions and demographic parameters. That is, for continuous data (e.g. HHS), the N, mean, median, standard deviation, minimum and maximum will be computed. For categorical data (e.g. gender), the frequency will be computed. If appropriate, the data will be presented by two cohorts in the Tritanium® Primary Acetabular Shell Study.

Descriptive statistics and statistical comparisons for important demographic, efficacy and safety variables will be provided in tables.

A survival analysis for revision of the acetabular component will be performed.

#### 9.4.2 Sample Size Calculation

A literature review shows that at 5 years of follow-up there is a 97.9% to 99.6% success rate in similar devices using revision or removal of the acetabular component as the defining factor. Based on these results, it should be a reasonable assumption that the base success rate of revision or removal of the Tritanium® Acetabular Shell will be approximately 99% at 5 years. Using a base success rate of 99% from the literature and a delta of 5%, it was calculated that 142 total cases implanted with the Tritanium® Acetabular Shell would be needed to prove non-inferiority with 95% power. With a minimum of 142 cases analyzed, the primary hypothesis of the study will be met if the lower bound of the 90% confidence interval for the 5-year success rate is greater than 94%. By factoring in a 20% lost to follow-up rate within a 5-year period, the required sample size increases to 177 cases. Cases will continue to be enrolled until a total of 240 cases are implanted with the Tritanium® Acetabular Shell; half of these cases will use the X3® polyethylene insert alone as the bearing surface and the other half will use the MDM™ liner coupled with a compatible ADM/MDM™ X3® insert as the bearing surface.

# **9.4.3 Interim Analyses and early Stopping Considerations** No interim analysis is planned.

### 9.4.4 Efficacy Patient Populations

### 9.4.4.1 **Efficacy**

#### Per protocol population:

The study population for analysis will include all subjects who receive the Tritanium® Acetabular Shell. This does not include cases censored from analysis or cases that are unavailable for evaluation at the 5-year primary endpoint.

The primary and secondary efficacy analyses will be based on the per protocol population.

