### 7.2 Surgery

Surgical details will be collected from the operative notes and at the time of surgery.

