### 9.1.2 Secondary Efficacy Parameters

The secondary efficacy parameters include:

- The usage of screw fixation
- HHS at the 1-, 3- and 5-year follow-up visits
- SF-12 scores at the 1-, 3- and 5-year follow-up visits
- LEAS at the 1-, 3- and 5-year follow-up visits
- EQ-5D at the 1-, 2-, 3-, 4- and 5-year follow-up visits
- Follow-Up Questionnaire annually in postoperative years 6-10

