## SURGICAL DETAILS

Submit Surgical Details CRF ONLY if surgery is performed and subject receives study device.

GENERAL INFORMATION					
SUBJECT	INITIALS:	SURG	GERY DATE:	SUBJECT ID:	
	The state of the s				
I SUBCICAL DETAILS		(DC	D-MMM-YYYY)		S. St. Phys.
I. SURGICAL DETAILS	D. MALICOLE I	DEDAID OD			
A. APPROACH  Anterior	B. MUSCLE I		REATTACHMENT REQUIR		TION USED?
Anterolateral	O No		which muscle group?	○ Yes	
O Posterior/ Posterola		A CHARLES TO COL	rnal Rotators eus Medius	○ No	
O Dual Incision	iteral	Othe	and the state of t		
() Lateral		_ othe			
D. INCISION LENGTH					
	E. DURATIO			F. ESTIMA	TED BLOOD LOSS
cm	Skin to Ski	n	minutes		cc
I. PROSTHESES					
G. PROSTHESES - Upload a copy of the con	nnonent lahel/s) implant	her	H. OTHER?	O Yes* O N	No
Acetabular Shell -	inponent tabel(s) implant		*If Yes, specify an	d upload a copy of the la	bel(s).
Go to Subject Informatio	n screen and enter data	in Products	tab. Add Row Other (S	Specify) Reference #	Lot#
	Reference #	Lot#	Reset	Specify) Reference #	LOT#
Acetabular Liner		II Nowe	×		
Acetabular Insert	Reference #	Lot#	Attitude (S.V.)	NAME OF TAXABLE PARTY.	
Acctabalal Insert	Reference #	Lot#			
Femoral Bearing Head	- HOIGIGING II	2001			
	Reference #	Lot#			
Femoral Stem					
I. BONE SCREWS USED?	○ Yes* ○ No				
*If Yes, specify and uploa					
Add Pow					
Reset	e# Lot:	#	J. INTRAOPERATIVE	COMPLICATION?	
X				E form. (a) Yes* (	No
				0	
			K. DISCHARGED TO:	: (Check One)	
			Skilled Nursing Fa	cility	
			Chronic Care Cent	ter	
			Rehabilitation Un	it	
			O Home		
			the Electric transfer of the second		
			Other: (Specify)		
			Discharge Date:		
I. COMMENTS				DD-MMM-YYYY	
II. COMMENTS					
	Reason for Save				
Verification / Cor	nfirmation Method				
			Cubacia		
0Aug2011 Ver 1 0			Submit		
9Aug2011 Ver.1.0		Pa	age 1 of 1		

[figure not shown]

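### Section 9.4.4.1 applies the 5-year availability condition to secondary outcomes observed earlier, and no planned analysis tests loss related to revision

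*Combined protocol and SAP*

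**What the plan says.** Section 9.4.4.1 starts from all subjects who received the shell and then narrows the set: "This does not include cases censored from analysis or cases that are unavailable for evaluation at the 5-year primary endpoint". The next sentence fixes its use: "The primary and secondary efficacy analyses will be based on the per protocol population".

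Section 9.1.2 lists among the secondary parameters "The usage of screw fixation" and "HHS at the 1-, 3- and 5-year follow-up visits", with SF-12 and LEAS at the same visits. Screw use is known on the day of operation. Section 7.2 says "Surgical details will be collected from the operative notes and at the time of surgery", and the Surgical Details form in Appendix E carries the item ("BONE SCREWS USED").

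For the primary endpoint, Section 9.1.4 says "A case success is defined as no incidence of revision or removal of the acetabular component within 5 years". Non-inferiority is supported if the lower bound of a 90% confidence interval exceeds 94%. Neither that section nor the Synopsis names the interval method. Section 9.1.4 adds: "The Kaplan-Meier survival curve of revision or removal of the acetabular component will also be displayed using SAS/PROC LIFETEST". Section 9.4.4.3 puts the survival analysis on all enrolled subjects who received the shell. Section 9.3 rules out imputation. Section 10.3 makes shell revision both a failure and a reason for termination. No sensitivity analysis for cases lost before 5 years appears anywhere.

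**The concern.** A condition that concerns the 5-year endpoint governs outcomes observed years earlier. A subject with a complete year-1 assessment who is lost in year 4 drops out of the year-1 comparison, and also out of a comparison of what was done in the operating theatre. The Tritanium group compared with the historical study then consists of people who stayed to 5 years. Nothing in the documents says that the control group is selected in that way, so the two groups may differ for a reason unrelated to the device.

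For the primary endpoint, the issue is what the plan can say about cases that leave. The completer proportion ignores them. The survival curve keeps their follow-up but has no decision rule, and it treats loss as unrelated to revision. If patients whose shells are revised elsewhere are the ones who stop attending, both summaries can favour the device and no planned analysis would show it.

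**Working it through.** **Inputs.** From 9.4.2: 240 implanted, 20% lost by 5 years, 99% assumed success, 5-point margin, 95% power. From 9.1.4: threshold 94% and a 90% interval, hence one-sided 5%. Assumptions made here: constant loss and revision hazards; revised cases kept as failures; exact (Clopper-Pearson) limits unless stated; 120 to 480 controls with equal variance, because the documents do not give the control size.

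**1. The plan's own figure.** n0 = [1.645√(0.94×0.06) + 1.645√(0.99×0.01)]² / 0.05² = 122.9. With continuity correction, (122.9/4)×[1 + √(1 + 2/(122.9×0.05))]² = 142.2, against 142 stated. Then 142/0.8 = 177.5, against 177 stated. The figure is reproduced, and it is a count of completers.

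**2. Records removed.** Completers at 5 years: 240×0.8 = 192.
- Screw use: 240 − 192 = 48 of 240.
- Year 1: 240×0.8^(1/5) = 229.5; less 192, about 38 of 230.
- Year 3: 240×0.8^(3/5) = 209.9; less 192, about 18 of 210.

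For 10% to 30% loss the ranges are 24 to 72, 19 to 56 and 9 to 26. The Synopsis words the screw objective for cluster-hole shells. If only those are compared, the count falls but the share stays one fifth.

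**3. Precision.** The planned tests compare with a control of size m, so the standard error of the difference grows by √[(1/192 + 1/m)/(1/n + 1/m)], where n is the number with data.

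| Outcome | n | m = 120 | m = 480 |
|---|---|---|---|
| Year 1 scores | 229.5 | 1.033 | 1.064 |
| Year 3 scores | 209.9 | 1.017 | 1.032 |
| Screw use | 240 | 1.041 | 1.080 |

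**4. Primary rate, loss independent of revision.** Let h = −ln(S)/5 and l = −ln(0.8)/5. The completer rate is A/[A + (h/(h+l))(1−A)], where A = exp(−5(h+l)). A true 99% reads 98.9%, and a true 94% reads 93.3%, so the bias is against the device. With 192 analysed, up to 5 failures pass, and power at a true 99% is 98.7%. In simulation at 30% loss it is still about 96%.

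**5. Tipping point.** Exact lower limits: 5/192 failures, 94.60% (pass); 8/240, 94.07% (pass); 9/240, 93.55% (fail). The conclusion therefore reverses once observed and unseen revisions total 9.

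| Observed among 192 | 0 | 1 | 2 | 3 | 4 | 5 |
|---|---|---|---|---|---|---|
| Unseen among 48 that reverse | 9 | 8 | 7 | 6 | 5 | 4 |

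With 2 observed, that is 7/48 = 14.6% of lost cases; with 5 observed, 4/48 = 8.3%.

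**6. Interval method.** With 6/192 failures the lower limit is 93.93% exact (fail), 94.07% Wilson (pass) and 94.81% Wald (pass).

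**7. Informative loss.** Simulated with 240 cases, 20% loss, and the revision hazard multiplied after loss. For a true rate of about 93 to 94%, exact completers falsely pass in roughly 2 to 3% of trials at 2-fold, 5% at 3-fold, 10% at 5-fold and 43% at 15-fold. These values move with the true rate. Fixed at 94.0% they are about 3, 5, 12 and 55%; fixed at 93.3%, about 1, 2, 7 and 44%. The documents give no basis for any multiplier.

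**The case against.** The exclusion names the 5-year primary endpoint, so a sensible analyst might apply it only there. Section 16 plans a publication at 3 years, when 5-year availability cannot yet be known and the literal rule could not be applied. This makes it plausible that the sponsor does not intend to drop early data. It does not override the explicit sentence that puts the secondary analyses on this population.

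The primary effect is small on the plan's own assumptions; that stands. Reversal with 2 observed revisions needs 14.6% of lost cases to have been revised, against about 1% expected. Section 10.3 requires three calls and a certified letter before a case is declared lost, and the Study Termination form asks whether the device was in place at last contact. These make reversal less likely, but they do not replace an analysis that shows how far the result is from it.

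Several stronger readings are tempting, and the documents do not support them:
- That every efficacy analysis excludes lost cases. The survival analysis (9.1.4, 9.4.1, 9.4.4.3) keeps them, and 9.2.1 with 9.4.4.2 reports revision rates without the 5-year condition.
- That the exclusion favours the device. With independent loss it does the reverse.
- That revised cases are dropped as unavailable. Sections 9.1.4 and 10.3 count them as failures; the plan should say so in 9.4.4.1.
- That a high false-claim rate has been shown. The 43% figure rests on an assumed 15-fold hazard.
- That Kaplan-Meier should replace the completer rate to gain power. At a true 98% and 20% loss its log-log limit passes in about 90% of trials, against 79% (exact), 82% (Wilson) and 92% (Wald) for completers, so any gain depends on the unnamed interval method. Nor does it protect against informative loss.

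**Conclusion.** The point holds, and the wording should be fixed. As written, one fifth of screw records and about 38 of 230 year-1 and 18 of 210 year-3 score sets go unused at the planned loss, and the Tritanium group is selected on later attendance. The precision cost is modest: standard errors of the difference are larger by about 3 to 6% (year 1), 2 to 3% (year 3) and 4 to 8% (screw use), given the assumed control size. The comparability of the two groups matters more.

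The primary rate is slightly conservative under independent loss, and power at 99% is adequate. The real gap there is that nothing planned tests loss related to revision. The tipping counts of 9 down to 4 need no assumed hazard, only exact limits and the 192/48 split. Any false non-inferiority rate under informative loss should be given as a range over the multiplier, not as one figure.

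**What to change.** 1. In 9.4.4.1, limit the 5-year availability condition to 5-year endpoints. Analyse 1- and 3-year scores in all subjects with data at that visit, and screw use in all implanted cases.
2. Add a tipping-point analysis on revisions among lost cases, in the form of the table in step 5.
3. Report the 5-year Kaplan-Meier rate with its 90% log-log lower limit in the 9.4.4.3 population as a supportive sensitivity analysis. The completer proportion remains the decision rule.
4. Name the interval method in 9.1.4 and the Synopsis. State that any case revised within 5 years counts as a failure and not as unavailable.
5. Reconcile the Synopsis objectives, 2.1.2 (Patient Outcomes) and 7.4, which tie the year 6-10 questionnaire to the primary objective or endpoint, with 9.1.4, which sets a 5-year rule, and 9.1.5, which uses the questionnaire for years 6-10 of the curve.

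The cost is a few sentences, one survival estimate and one table. No new data are needed. Kaplan-Meier still assumes non-informative loss, so item 3 does not replace item 2.
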